4. During the 14-day data collection period, data from the EMA will be collected using EMA software platform on a personal smartphone (iOS or Android) and EMA software platform.⁷³ Each morning, participants will receive an EMA survey concerning asthma symptoms and a reminder to use their spirometer. Additionally, EMA surveys addressing disinfectant use, asthma symptoms, and spirometry will occur randomly twice/day (6am – 10pm) or tailored for those working off hours (Appendix).
5. A custom interface between the EMA platform and the Awair indoor air quality monitor will alert participants when levels of indoor VOCs or particulates are detected outside the optimal range (Table 1). The air quality monitor will communicate with the EMA platform using publicly available application programming interface (api). Upon notification from the Awair, the EMA will signal the participant to complete a brief survey on disinfectant use/air particulate exposure (depending on the alert), current asthma symptoms, and proximity to the Awair (Appendix). The EMA will then direct participants to use the spirometer. Participants experiencing symptoms will be guided to follow their asthma action plan/provider instructions.
6. Thirty minutes after VOC/PM_{2.5} notification, a second EMA notification will be sent for participants to complete a survey on mitigation strategies, respiratory outcomes, and spirometry use if not already completed (Figure 4).
7. Research personnel will monitor use of these devices/apps and contact participants if a 24-hour gap in data is noted to address concerns and determine acceptability. Research team members will check-in with each participant at about the 7-day mark to address technical concerns and ease of use.

8. At the end of the 14 days, participants will complete a short acceptability, appropriateness, and feasibility REDCap survey. A random sample of 20 participants will be interviewed to provide further insights.
9. Participants will be asked to return the Awair in the provided mailer. The Awair will be fully disinfected per manufacturer's directions. Participants will keep the Zephyr_x spirometer as an incentive.

Baseline Measures

The following measures will be administered at baseline via REDCap:

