- *EMA survey triggered by VOCs/PM_{2.5} greater than optimal range as detected by the Awair* will query asthma symptoms, lists of probable sources of elevated VOCs or PM_{2.5}.
- *EMA survey 30-minutes after Awair air quality notification* queries mitigation strategies used (from lists) and asthma symptoms.
- *Home spirometer use* (Yes:No) queried in each EMA survey

Home spirometer. FEV₁% predicted– a standard metric of lung function for those with asthma.

Seven-Day check-in. Open-ended questions to identify any trouble-shooting areas, determine if adjustments need to be made, and assess ease of use of the app/devices. Interactions will be recorded and reviewed by the research team for patterns and to identify any adjustments that are needed.

Participant feasibility assessment. At the end of the 14-day data collection period, participants will be asked to respond to a short REDCap survey assessing acceptability, appropriateness, and feasibility of the indoor air quality monitor, EMA notifications, and the home spirometer with response ranging from 1=completely disagree to 5=completely agree. A random sample of 20 participants will be interviewed to further explore these factors using open-ended questions such as "Tell us what you liked/didn't like about the indoor air quality monitor", "Describe the strengths/concerns about the survey you received about your home indoor air quality".

Data Analysis

Each day of observation will be divided into four 4-hour periods between 6 a.m. and 10 p.m. Data from a given period will be considered as follows:

1. Period specific data from all event-contingent EMA prompts [prompts triggered by high indoor air VOC/PM_{2.5} readings] will be analyzed. If multiple event-contingent prompts were answered, data will be averaged across all event-contingent prompts during that period.
2. Data from all answered baseline and random [signal-contingent] EMA prompts will be considered.

Aim 1. For this aim, we will assess:

1. Compliance with the EMA prompts as indicated by the frequency of responses to prompts, specifically:
 - a. # of responses (complete:incomplete)/number of prompts
 - b. # times spirometer used/number of prompts
 - c. # times environment modified/number of event-contingent prompts
2. Compliance as described in 1a-1c by 4-hr each period.

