We will also assess the duration the indoor air quality monitor is used by each participant. The quantitative participant feasibility assessment of acceptability, appropriateness, and feasibility will be analyzed descriptively. In addition, we will examine differences in use/acceptance by participant characteristics (e.g., age, asthma symptoms, overall health, education, etc). Qualitative interview data will be transcribed, uploaded into Dedoose qualitative analysis software for content analysis.

Aim 2a: We will collect baseline data on the current frequency and degree of disinfectants/cleaners and exposure to environmental triggers (e.g., secondhand smoke). We will capture real-time self-reported data on disinfectant use throughout the study period. We will determine the prevalence of disinfectant/cleaner use and frequency (% EMA prompts at which disinfectant/cleaner use is reported). We will obtain data from the Awair dashboard to determine the number of times VOCs and PM_{2.5} levels exceed optimal levels, average daily levels, average levels per time period, and fluctuations in VOC and PM_{2.5}. We will identify possible environmental triggers that contribute to high levels of VOCs and PM_{2.5} leading to event-contingent prompts.

[figure not shown]
Aim 2b: We will determine baseline level of asthma control as measured by the ACT. We will use EMA to determine the level of asthma control over the study period as indicated by (a) asthma symptoms reported at each prompt and over the 14 days; (b) number of time-periods during which an EMA prompt is sent and participants report asthma symptoms; and (c) lung function as measured by FEV₁% predicted at each prompt. Asthma control will also be evaluated using EMA by exploring differences in variability in lung function.

Aim 3: Data collected using the EMA approach are multilevel with time windows (level 1) nested with individuals (level 2). The exposure variables will include: (1) Baseline self-reported use and frequency of disinfectant/cleaner use and PM_{2.5} exposures; (2) Number of times VOC and PM_{2.5} levels exceed the threshold for the optimal readings per week; and (3) Average scores of VOC and PM_{2.5} levels in the time windows considered in the analysis. The outcome variables we will consider include occurrence of any asthma symptoms, inhaler use, and FEV₁% predicted (within 30 minutes of each EMA prompt).

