We will use multi-level binary logistic regression to examine the associations of the exposure variables with the binary outcome variables. We will use multilevel linear regression to examine the associations of the exposure variables with FEV₁% predicted. We will control for level 1 variables (time of day, day of week) and level 2 variables (baseline asthma symptoms, demographic characteristics, and psychosocial characteristics). Using available time stamps from the indoor air quality monitor, EMA, and the spirometer, we will also explore average lag time between an event-contingent prompt and self-reported asthma symptoms using multilevel survival analyses.

Summary

The proposed study has several strengths. First, our study is innovatively addressing the increased use of disinfectants during COVID-19 in adults with asthma. The study builds on an ongoing study and will be conducted with individuals who have agreed to be recruited for future studies and facilitate recruitment. Furthermore, participants will be drawn from a wide geographic area in the US which increases broad representation of participants. Moreover, we will uniquely gather real time environmental exposure data and indicators of asthma control in unregulated indoor residential space without actual in-person contact. Finally, findings from this study have the potential to impact recommendations for indoor use of disinfectants/cleaners for those with asthma and will guide further research.

References

1. Center for Disease Control and Prevention. Asthma. FastStats web site. <https://www.cdc.gov/nchs/faststats/asthma.htm>. Published 2018. Accessed Date.
2. Center for Disease Control and Prevention. AsthmaStats. https://www.cdc.gov/asthma/asthma_stats/default.htm. Published 2020. Accessed Date.
5. Center for Disease Control and Prevention. Coronavirus (COVID-19). <https://www.cdc.gov/coronavirus/2019-nCoV/index.html>. Published 2020. Accessed Date.

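### The Aim 2b(b) count of symptom periods has no denominator, so it tends to rise with air-quality alerts at an unchanged symptom rate; the averaging rule for Yes/No answers also conflicts with the Aim 3 outcome wording

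*Combined protocol and SAP*

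**What the plan says.** Prompts come from three sources (Procedures, items 4 to 6): one morning survey, two random surveys a day, and a survey whenever VOCs or PM2.5 leave the optimal range. Thirty minutes after an alert, "a second EMA notification will be sent for participants to complete a survey on mitigation strategies, respiratory outcomes" and spirometry. No cap on alerts is stated. EMA survey items lists Yes/No symptom questions for both the alert survey and the 30-minute survey.

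Data Analysis cuts the day from 6 a.m. to 10 p.m. into four windows, which gives 4 x 14 = 56 per person. Its first rule concerns event-contingent prompts: "If multiple event-contingent prompts were answered, data will be averaged across all event-contingent prompts during that period". The second rule says that answered baseline and random prompts are considered, without saying how they are combined.

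Aim 2b lists several indicators of control. Item (a) is "asthma symptoms reported at each prompt and over the 14 days". Item (b) is the "number of time-periods during which an EMA prompt is sent and participants report asthma symptoms". By contrast, Aim 2a reports disinfectant use as a percentage of "EMA prompts at which disinfectant/cleaner use is reported".

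Aim 3 makes time windows level 1 and individuals level 2. Its outcomes are any asthma symptom, inhaler use and FEV1% predicted, followed by the bracket "within 30 minutes of each EMA prompt". It adds: "We will use multi-level binary logistic regression to examine the associations of the exposure variables with the binary outcome variables".

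**The concern.** **Aim 2b(b).** The phrase about a prompt being sent defines which periods are eligible, but nothing divides by them. The number of eligible periods, and of symptom questions within them, depends partly on how often the monitor alarms. The count therefore mixes symptom frequency with alert frequency. Two homes with equal symptom rates would look differently controlled if one had more alerts, and this measure would go into the preliminary data for the powered study.

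**Averaging.** One Yes and one No in a window average to 0.5. If that average is the window-level outcome, the stated binary model does not take it, and no rule turns it back into 0 or 1. Some software fits fractions without complaint, so the problem could pass unnoticed.

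**Working it through.** The plan states no expected count, symptom rate or alert rate, so there is no figure of its own to reproduce.

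**Inputs from the documents:** 14 days, 4 windows a day, 1 morning prompt, 2 random prompts, and an alert survey plus a 30-minute survey per alert.

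**Assumptions:** symptom probability p = 0.15 at every prompt; morning prompt in the first window; random prompts uniform over the four windows; alerts Poisson with mean m/4 per window; both alert questions in the same window; all prompts answered; a period counts if any answer is Yes. The correlation rho between two answers in one window is varied. Each answer equals a window state Z ~ Bernoulli(p) with probability a = sqrt(rho), and is otherwise an independent Bernoulli(p). Then

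P(any Yes in k answers) = 1 - [(1-p)(1-(1-a)p)^k + p(1-a-(1-a)p)^k].

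**Step 1, prompted periods.** A window after the first has no random prompt with probability (3/4)^2 = 0.5625.
- 0 alerts/day: 14[1 + 3(1 - 0.5625)] = 32.4
- 3 alerts/day: 14[1 + 3(1 - 0.5625e^-0.75)] = 44.8

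**Step 2, answers always agree (rho = 1).** The count is p times prompted periods: 0.15 x 32.4 = 4.9 and 0.15 x 44.8 = 6.7. The ratio is 44.8/32.4, or 1.39 before rounding the inputs, whatever p is.

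**Step 3, independent answers (rho = 0).** The chance of no Yes from the random prompts is (1 - 0.15/4)^2 = 0.9264. From alerts at 3/day it is exp[-0.75(1 - 0.85^2)] = 0.8121. From the morning prompt it is 0.85.
- 0 alerts/day: 14[(1 - 0.85 x 0.9264) + 3(1 - 0.9264)] = 6.1
- 3 alerts/day: 14[(1 - 0.85 x 0.9264 x 0.8121) + 3(1 - 0.9264 x 0.8121)] = 15.4, a ratio of 2.55

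**Step 4, in between, and other symptom rates.**

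| rho | Symptom periods, 0 vs 3 alerts/day | Ratio | Divided by prompted periods |
|---|---|---|---|
| 0 | 6.1 vs 15.4 | 2.55 | 18.7% vs 34.5% |
| 0.7 | 5.2 vs 9.0 | 1.73 | 16.1% vs 20.0% |
| 0.9 | 5.0 vs 7.5 | 1.50 | 15.4% vs 16.6% |
| 1 | 4.9 vs 6.7 | 1.39 | 15.0% vs 15.0% |

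At p = 5% the ratio runs from 2.83 (rho = 0) to 1.39 (rho = 1); at p = 30%, from 2.21 to 1.39. Dividing by prompted periods is a full repair only when answers always agree.

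**Step 5, would a pooled prompt rate do?** Scheduled answers number 3 x 14 = 42, and alert answers at 3/day number 3 x 2 x 14 = 84. With equal symptom probability, Yes over answers is 15% at any alert rate. If the probability is 15% at scheduled prompts and 30% at alert times (assumed), the pooled rate is (42 x 0.15 + 84 x 0.30)/126 = 25%, against 15% in a home with no alerts. Pooling would then still depend on how many alerts a home has.

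**Step 6, fractional averages.** Assume 1.5 alerts/day, 80% response and p = 0.15, and take the share of windows with an answered event-contingent prompt. If the follow-up is not event-contingent, answered alerts per window are Poisson with mean 0.375 x 0.8 = 0.3. At rho = 0:
- P(any answered) = 1 - e^-0.3 = 0.2592
- P(any Yes) = 1 - e^-0.045 = 0.0440
- P(all answers Yes) = e^-0.3(e^0.045 - 1) = 0.0341
- Share = (0.0440 - 0.0341)/0.2592 = 3.8%

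The share falls to 0.4% at rho = 0.9. If the follow-up counts as event-contingent, it is 21% at rho = 0 and 2.2% at rho = 0.9.

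**The case against.** Aim 2b(b) is one descriptive indicator among several. ACT, symptoms at each prompt, FEV1% predicted and lung-function variability are also reported. Per-prompt symptoms from item (a), with the Aim 1 prompt counts, would let an analyst build a rate. No test or decision uses the count, and the plan does not say homes will be ranked on it. All of that stands and limits the severity. It does not repair (b), which is listed separately as an indicator of control and is not linked to those denominators. The size rests wholly on assumed rates, and the larger ratios need answers in one window to disagree often, which is unlikely for questions 30 minutes apart. The 39% rise needs no disagreement.

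On averaging, the objection is stronger. An outcome defined as any symptom, with the bracket "within 30 minutes of each EMA prompt", can be read as 0/1 per prompt, in which case the averaging rule does not reach it. The bracket might attach only to FEV1% predicted, and level 1 is still the window, so the text does not settle the matter. The plan's own gloss on event-contingent prompts, those triggered by high readings, favours leaving the follow-up out, which gives the smaller range.

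A reader might infer that the Aim 3 associations are biased. The documents do not support that. It would require scoring a window as positive on any Yes, which the plan does not state, and the Aim 2b(b) count is not a listed Aim 3 outcome. Nor do they support saying that the logistic model will certainly receive fractions.

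**Conclusion.** The Aim 2b(b) point holds on the text: as written, the count tends to rise with alerts when symptom frequency does not change. Under the stated assumptions the rise from 0 to 3 alerts a day is between 39% and 2.55-fold. It is a rise in expectation: an alert in a period that already has a symptom report adds nothing, and 56 is the ceiling.

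The averaging point is a conflict between sections, not a certain error. At 15% symptoms it touches about 0.4% to 3.8% of windows with an answered event-contingent prompt if the follow-up is excluded, and about 2% to 21% if it is included.

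Aim 1 is unaffected, Aim 3 is exploratory, and Aim 2b(b) is descriptive. Severity is minor to moderate.

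**What to change.** **Aim 2b(b).** Make the main measure the share of answered scheduled (morning and random) prompts with symptoms. Report the same share for alert and follow-up prompts separately. Do not pool the two as the main rate (Step 5). If the period count is kept, show it with prompted periods and prompts answered.

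**Averaging and Aim 3.** Limit averaging to continuous measures such as FEV1% predicted, and state whether the 30-minute survey is event-contingent. Analyse Yes/No outcomes as one 0/1 row per answered prompt, linked to that window's exposure, with clustering within person and a small-sample correction for about 50 people. Add a sensitivity analysis restricted to scheduled prompts. The correction matters. In a null simulation of such a model (50 people, 56 windows, GEE exchangeable within person, 300 runs per setting), rejection at rho 0, 0.5 and 0.9 was 9.3%, 6.7% and 9.3% with robust errors, and 8.3%, 5.0% and 6.0% with bias correction and 49 degrees of freedom. It helps but may not fully restore 5%.

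**First reconcile** two lines under EMA survey items. One has symptoms asked at every survey. The other can be read as asking them in random surveys only after a Yes on disinfectant use. Procedures, item 4, favours the former. The answer determines the scheduled-prompt denominator.

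**Cost.** Analysis-plan wording, since monitor, EMA and spirometer data already carry time stamps. The downsides are slightly more analysis work, fewer answers in the main Aim 2b(b) rate, and more rows from homes with many alerts in the Aim 3 model.

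### Aim 1 has no measure of whether out-of-range monitor readings generated event-contingent prompts, or how quickly

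*Combined protocol and SAP*

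**What the plan says.** Procedures, step 5, describes the component at issue: "A custom interface between the EMA platform and the Awair indoor air quality monitor will alert participants when levels of indoor VOCs or particulates" leave the optimal range given in Table 1. The alert calls for a short survey and a spirometry manoeuvre, and step 6 adds a second survey 30 minutes later.

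Data Analysis, Aim 1, lists three compliance ratios:

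- 1a: the number "of responses (complete:incomplete)/number of prompts"
- 1b: the number of "times spirometer used/number of prompts"
- 1c: the number of "times environment modified/number of event-contingent prompts"

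Item 2 repeats them by time of day: "Compliance as described in 1a-1c by 4-hr each period".

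Aim 1 has further measures. On the monitor: "We will also assess the duration the indoor air quality monitor is used by each participant". On the end-of-study survey: "The quantitative participant feasibility assessment of acceptability, appropriateness, and feasibility will be analyzed descriptively". On interviews, under Participant feasibility assessment: "A random sample of 20 participants will be interviewed to further explore these factors using open-ended questions".

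The count of exceedances of the optimal range is taken from the monitor dashboard under Aim 2a and is reused as an exposure in Aim 3. It is not used in Aim 1. The only lag analysis, at the end of the Aim 3 text, runs from an event-contingent prompt to reported symptoms.

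**The concern.** Specific Aims, Innovation and Research Design all present the real-time linking of monitor, EMA and spirometer as what is new and what Aim 1 is to test. For triggered assessment to work, two things must happen: a high reading must generate a prompt, and the participant must respond to it. The Aim 1 ratios address the second step only. If the link is slow or drops readings, the ratios do not show it.

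Two things are at stake. First, the study is meant to supply preliminary data for a powered study, which could plan on a yield of triggered surveys per exceedance that was never estimated. Second, each missed exceedance loses what the survey would have collected: the likely source of the high reading (Aim 2a), and the symptom report and FEV1 value tied to that moment (Aims 2b and 3).

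**Working it through.** The documents give no feasibility threshold, sample-size derivation or power figure for Aim 1, so there is no stated figure to reproduce. The check is whether the planned ratios can respond to a failure of the link.

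**Inputs from the documents**

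- Scheduled prompts (Procedures, step 4): one each morning plus two at random, so 3 × 14 = 42 per participant, or 42 × 50 = 2,100 if all 50 take part.
- Triggered prompts (steps 5 and 6): two per alert.
- Monitor readings (Awair Omni paragraph): one every 10 seconds, so 8,640 a day and 8,640 × 14 = 120,960 per participant.

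**Assumed quantities.** E = out-of-range episodes per participant (5, 14 or 42); f = share of episodes that generate a prompt (1, 0.5, 0.1 or 0); r = response rate to prompts, taken as equal for scheduled and triggered prompts (1.0 or 0.8).

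**Formulas**

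- Prompts = 42 + 2Ef
- Ratio 1a = r(42 + 2Ef) / (42 + 2Ef) = r
- Share of episodes with an answered survey = f × r

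The results are the same for every E:

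| f | 1a, r = 1.0 | episodes captured, r = 1.0 | 1a, r = 0.8 | episodes captured, r = 0.8 |
|---|---|---|---|---|
| 1 | 1.00 | 1.00 | 0.80 | 0.80 |
| 0.5 | 1.00 | 0.50 | 0.80 | 0.40 |
| 0.1 | 1.00 | 0.10 | 0.80 | 0.08 |
| 0 | 1.00 | 0 | 0.80 | 0 |

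Ratio 1a does not contain f. Restricted to triggered prompts, 1a is also r until f = 0, where it becomes 0/0: undefined, not low. Ratio 1c has the same denominator and behaves in the same way. If response differs between scheduled and triggered prompts, 1a shifts with the mix of prompts, but it still does not measure f.

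For an illustrative range of 60-90% conversion with 80% response: 0.60 × 0.80 = 0.48 and 0.90 × 0.80 = 0.72, against a reported 1a of 0.80.

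**Could another planned element measure f or the delay?**

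- Monitor-use duration: no, since the monitor can run while the link is down.
- Contact after a 24-hour data gap (step 7): not reliably, since the three scheduled surveys a day continue.
- Lag analysis: no, since it starts at the prompt.
- Ratings, 7-day check-in, interviews: they may bring a fault to light but give no rate. The monitor displays VOC and PM2.5, so some participants could notice a missing alert; others would not know of it.

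**Would an added conversion rate be precise enough?** Half-width = 1.96 × √[p(1 − p)/n_eff], with n_eff = 50E / [1 + (E − 1) × ICC]. Assume p = 0.9 and all 50 contributing.

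- E = 42, ICC = 0: n_eff = 2,100, half-width 0.013.
- E = 5, ICC = 0.5: n_eff = 250/3 = 83.3, half-width 0.064.

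Over E = 5 to 42 and ICC = 0 to 0.5, the 95% half-width is 1.3 to 6.4 percentage points, which is usable.

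**The case against.** The best case for the plan is that Aim 1 is broader than its ratios, and that the ratios are labelled compliance and not system performance. Devices and apps are tested at set-up, there is a 3-day run-in for troubleshooting, staff watch device and app use, and the 7-day check-in is recorded and reviewed for patterns. The survey rates the EMA notifications themselves, and one sample interview question concerns the air-quality survey. This makes a long, unnoticed failure less likely. It stands, but none of it yields a conversion rate or a delay.

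Several stronger readings are tempting and are not supported:

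- *Aim 1 looks only at responses to prompts.* It also has monitor-use duration, ratings and interviews.
- *A failing system would be declared feasible.* No pass mark is stated, so nothing is scored as feasible or not.
- *The denominator is prompts that arrived.* The text says only prompts. If that means prompts sent, one lost on the way to the phone counts as non-response and lowers 1a. An exceedance that never generated a prompt is invisible on either reading.
- *Late prompts vanish.* They count in 1a-1c; only their delay goes unmeasured.
- *Aims 2a and 3 lose the high-exposure moments.* Exceedance counts and levels come from the dashboard whether or not a prompt fires, and Aim 3 also uses outcomes from scheduled prompts.

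A fair caution about the remedy also stands. The monitor is to be kept where the participant sleeps at night, while the analysis periods run from 6 a.m. to 10 p.m. A yield over all hours would count sleep as failure.

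**Conclusion.** The point holds as a gap in measurement. Nothing in Aim 1 quantifies whether out-of-range readings became prompts, or how fast, and ratios 1a-1c can be high, even 100%, at any level of conversion. The algebra needs no assumption about the true conversion rate, only that prompts form the denominator and that scheduled and triggered prompts are answered alike.

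The size of any shortfall is unknown. The 48-72% range is multiplication of assumed rates (60-90% conversion, 80% response) and is not evidence that the link will fail. The loss is confined to source identification and to symptom and FEV1 data around missed exceedances.

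The Appendix and the figures were not in the text examined. An alert rule may be given there, and this conclusion is limited to the sections cited. The change is worth making because it is cheap and alters what Aim 1 can conclude about triggered EMA.

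**What to change.** Before analysis, define an out-of-range episode: a rule for grouping the 10-second readings that matches the alert logic, including how repeat alerts are handled. Then add two measures to Aim 1, beside 1a-1c:

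1. Episodes that generated a prompt divided by all dashboard episodes, with the median delay from reading to prompt.
2. End-to-end yield: episodes with both an answered survey and an FEV1 value, divided by all episodes.

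Report both for 6 a.m. to 10 p.m., or the participant's tailored hours, and show night-time episodes separately so that sleep is not counted as interface failure. State whether the number of prompts means generated, sent or delivered. Base the statement on feasibility of triggered EMA on both measures together with the response rate.

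Cost: a short definition and a time-stamp merge of monitor, EMA and spirometer records. Aim 3 already relies on time stamps from all three, and CSV export is stated for the monitor and the spirometer; the EMA prompt log must be obtained as well. No new participant data are needed. The reported feasibility may look less favourable.
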